2.1.2 Disposition of patients

The following patient disposition details will be summarized by subgroups and overall, and will include the number and percentage of patients:

- screened
- treated at V2
- included in the each study population (FAS, PPS, SAF)
- who completed the study
- who prematurely withdrew, including a breakdown of the primary reasons for withdrawal

All screened patients will be listed indicating their eligibility to each analysis set and reasons for exclusion from the analysis sets as appropriate.

Eligibility details, individual reasons for withdrawal and protocol deviations details will be listed separately.

2.1.3 Protocol deviations

Protocol deviations (PDs) are collected as per the latest version of the VAP Module 3 - Protocol Deviations (see Appendix 2). This document gives a full list of possible PDs, including whether they are programmatically or manually derived, as well as Severity/Analysis classification codes to be assigned to each PD. Rules for patient classification in the analysis sets based on PDs are as follows:

Protocol deviations and impact on analysis

Code	VAP de-code	Impact on analyses
0	Exclude from all efficacy analysis (including ITT)	Exclude patient completely from the FAS and Per-Protocol Sets.
1	Exclude from Per-Protocol analysis	Exclude patient completely from Per-Protocol Set.
2	Exclude from data analysis from this date	Data from this date/visit onwards excluded from per protocol analyses (patient not excluded from population).

49 Report relevant protocol deviation – Include in all analysis
include in all analyses

A protocol deviation meeting will be organized. The criteria and determination of clinically relevant protocol deviations and patient specific identification of data to be excluded from the PPS following this meeting will be databased and finalized prior to database lock.

All protocol deviations will be listed. All responses to the screening and baseline log will also be listed.

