2.1 Patients and treatments

2.1.1 Analysis sets

Assignment of patients to analysis sets will be agreed between the study statistician and the Sponsor prior to database lock, once all study data are available and verified. All efficacy analyses will be performed on the study eye. For visual acuity tests, the results for the fellow eye (non-study eye) will also be summarized for reference.

Full Analysis Set (FAS): The FAS consists of all patients who received at least one application of study treatment in the study eye, have baseline and have at least one post-baseline assessment for CSRT. Following the intent-to-treat principle, patients will be analyzed according to the treatment assigned. No data will be excluded from the FAS analyses because of protocol deviations.

Per Protocol Set (PPS): The PPS consists of all patients in the FAS who followed the assigned treatment and completed the study without clinically significant protocol deviations.

Safety Set (SAF): The SAF consists of all patients who received at least one application of study treatment in the study eye and had at least one post-baseline safety assessment.

All efficacy evaluations will be carried out on the Full Analysis Set and all safety evaluations will be carried out on the Safety Set. For sensitivity purposes, the primary analysis will be repeated using the Per Protocol Set. Any major discrepancies in the results across analyses will be investigated as necessary.

In addition, 2 subgroups of patients are defined:

- Group 1. Primary treatment failure (PTF)
- Group 2. Suboptimal treatment response (STR)

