2.2.1.2 Descriptive analyses

The change in CSRT from baseline to Day 90 will be summarized together with the 95% CI for the mean and absolute values of CSRT at baseline and at Day 90.

In the event that CSRT is missing for Day 90, the analysis will follow an LOCF (Last Observation Carried Forward) approach for the FAS.

The primary analysis will be performed on the FAS.

For sensitivity purposes, the primary analysis will be repeated using the PPS.

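### SAP 2.1.3 lets a code 0 protocol deviation remove a patient from the FAS, which SAP 2.1.1 and protocol 9.1 rule out; the effect on the primary result is unknown and may be nil

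*SAP*

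**What the plan says.** SAP 2.1.1 and protocol 9.1 give the same FAS: every patient treated at least once in the study eye who has a baseline and at least one later CSRT value. Both invoke the intent-to-treat principle and then state: "No data will be excluded from the FAS analyses because of protocol deviations".

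SAP 2.1.3 refers to VAP Module 3 for the full list of possible deviations and the "Severity/Analysis classification codes to be assigned to each PD". It then tabulates what each code does to the analysis sets. Code 1 removes the patient from the per-protocol set (PPS). Code 2 drops data from a given date onwards, in per-protocol analyses only. Code 49 changes nothing. Code 0 alone reaches the FAS: "Exclude patient completely from the FAS and Per-Protocol Sets". Its de-code says expressly that the exclusion extends to ITT.

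On use of the sets, SAP 2.2.1.2 says "The primary analysis will be performed on the FAS", and SAP 2.2.2.2 puts the secondary efficacy analyses on the FAS too. On procedure, SAP 2.1.1 says "Assignment of patients to analysis sets will be agreed between the study statistician and the Sponsor prior to database lock". SAP 2.1.2 provides a listing of all screened patients with "reasons for exclusion from the analysis sets as appropriate".

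**The concern.** The population for the primary analysis should follow from one rule, and here two rules give opposite answers for the same patient. The trial is open-label and single-arm, and sets are assigned once all study data are available. In that setting an unambiguous membership rule is the main protection against exclusions that depend on outcome.

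One type of deviation shows why the code matters. The introduction to SAP section 2 says the deviation review will flag patients whose baseline reading precedes study start by more than 3 days. That bears directly on the change in CSRT, and the code it receives is not visible. If it were code 0, the patient would leave the primary analysis. If it were code 1, the patient would stay.

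The planned sensitivity analysis could not show the effect of a code 0 removal. SAP 2.1.1 says "The PPS consists of all patients in the FAS who followed the assigned treatment", so a patient removed from the FAS cannot reappear in the PPS.

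**Working it through.** The plan gives no figure for this point, so the check is mainly a comparison of rules.

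**Step 1. Apply both rules to each kind of patient with a code 0 deviation.**

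| Patient | FAS under SAP 2.1.1 and protocol 9.1 | FAS under SAP 2.1.3 | PPS under SAP 2.1.3 | Safety Set |
|---|---|---|---|---|
| Fails one of the three FAS conditions | out | out | out | not affected by the code |
| Meets all three conditions | in | out | out | not affected by the code |

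The rules disagree only in the second row.

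**Step 2. Look for a rule of precedence.** The pre-lock agreement in SAP 2.1.1 says who decides and when, but not by which criterion. The deviation meeting in SAP 2.1.3 is described only in terms of data to be left out of the PPS. The visible entries in the SAP's list of changes from the protocol concern fluid and cyst measures, and two entries are redacted. No visible text settles the second row.

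**Step 3. Trace where a second-row patient would still appear.** The patient would be absent from the primary analysis (FAS), its repeat (PPS) and the secondary efficacy analyses (FAS). Code 0 does not touch the Safety Set, which carries exposure (SAP 2.1.7) and safety (SAP 2.4). The introduction to SAP section 2 lists all data for all screened patients. The removal would therefore be visible, but its effect on the CSRT result would not be estimated.

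**Step 4. Scale only.** The inputs are SD 102 µm (protocol, Amendment 2) and N = 124 (protocol section 4).

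- The 95% CI half-width is t(0.975, n−1) × 102/√n. It is 18.1 µm at n = 124, and 18.4, 18.6 and 19.1 µm if 3, 6 or 12 patients (assumed counts) are removed. Precision hardly changes.
- Removing k patients whose mean CSRT change differs by d from that of the rest shifts the mean by k × d/N. One patient with d = 40 µm gives 1 × 40/124 = 0.3 µm. Twelve patients with d = 80 µm give 12 × 80/124 = 7.7 µm. With the SAP's N of 150, the same two cases give 0.3 and 6.4 µm.
- The direction follows the sign of d. Removal unrelated to outcome gives no expected shift.

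The values of k and d are assumptions with no source in the documents. Nothing suggests that as many as twelve patients would be affected. These figures show how a shift would scale; they do not estimate one.

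**The case against.** Four arguments can be made for the plan.

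- **The code list is specified, only not visible.** VAP Module 3 assigns the codes, and the supplied text shows only its title. Code 0 may apply to no deviation, or only to patients who already fail the FAS definition. This stands, and it limits any claim about effect. It does not remove the contradiction, because SAP 2.1.3 presents code 0 as an exclusion caused by a deviation.
- **The FAS sentence may concern data, not membership.** The code table itself separates the two, since code 2 drops data but keeps the patient. On that reading, the sentence only bars truncating the data of FAS members. This does not hold: the FAS is all patients who meet three conditions, and removing a patient removes all of that patient's data.
- **Assignment is agreed before lock, and exclusions are listed with reasons.** Both are real safeguards for timing and transparency. Neither says whether a code 0 patient who meets the FAS definition belongs in the FAS.
- **The departure may be declared in a redacted entry.** That is possible. A declared departure would still leave SAP 2.1.1 at odds with SAP 2.1.3.

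A reader might also infer that the primary result is biased, that the sponsor has changed the FAS without saying so, or that code 0 patients drop out of every planned analysis. The documents support none of these. The code 0 list is not visible, two declared changes are redacted, and the patients remain in the Safety Set and the listings.

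**Conclusion.** The contradiction is in the current text and does not depend on any assumption: SAP 2.1.3 prescribes an exclusion from the FAS that SAP 2.1.1 and protocol 9.1 forbid. It concerns the set used for the primary and secondary efficacy analyses, so it should be corrected before database lock.

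The effect on the primary result is unknown and may be nil. It is nil if no code 0 entry can apply to a patient who meets the three FAS conditions. Otherwise it depends on how many such patients there are and how their CSRT change differs from the rest, and the documents give neither. The issue is who is in the primary population, not the precision of the estimate.

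**What to change.** Before database lock:

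1. State in SAP 2.1.3 that code 0 applies only to patients who do not meet the three-condition FAS definition.
2. Review the code 0 entries in VAP Module 3 one by one. Recode to code 1 any that could apply to a patient who meets the definition, with matching wording in both documents.
3. If a specific entry must still lead to FAS exclusion (for example, no valid consent), keep code 0 for it. Name it in SAP 2.1.1 as the only exception and record it as a change from protocol 9.1. Where the data may be used, repeat the primary analysis with those patients included.

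Simply redefining code 0 as a PPS exclusion would work less well. It would duplicate code 1 and leave no code for a justified exception.

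The cost is one sentence in SAP 2.1.3 and a review of the code 0 entries. If an exception is kept, add one line in SAP 2.1.1, one entry in the list of changes and at most one repeat analysis. No new data are needed. If no code 0 entry affects a patient who meets the FAS definition, the results do not change.

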2.1.4 Demographic and baseline characteristics

The following demographic and baseline characteristics, collected at screening, will be summarized by subgroup and overall for the FAS: age, sex, height, weight, body mass index (BMI), predominant race, and ethnicity. All demographic and baseline characteristics will be listed.

Descriptive statistics of the baseline value for the following continuous efficacy endpoints will be provided by subgroup and overall for the FAS, including a count of the number of missing readings/records:

- From optical coherence tomography (OCT):
 - Central subfield retinal thickness (CSRT) (*GRADE*: CSRTTHK)
 - Subfoveal Retinal Thickness (SRT) (*GRADE*: SUBFOVTK)
 - Central Subfield Retinal Volume (CSRV) (*GRADE*: CSRVVOL)
 - Subfoveal Choroidal Thickness (*GRADE*: SUBCHTK)
 - Maximum height of IRC (*GRADE*: IRCHEIGHT)
 - Maximum height of pigment epithelial detachments (PED) (*GRADE*: PEDHEIGHT)
 - Maximum diameter of PED (*GRADE*: PEDDIAM)
- From visual acuity: best-corrected visual acuity (BCVA) for study eye and fellow eye separately

Categorical summaries (Number and %) of the baseline results for the following efficacy endpoints will be provided by subgroup and overall for the FAS, including a count of the number of missing readings/records:

- From OCT:
 - OCT quality (OS – Oculus sinister or left eye (*GRADE*: OCQUALOS) and OD oculus dexter or right eye (*GRADE*: OCQUALOD))
 - Acceptability of OCT submission (*GRADE*: OCTSUB)
 - Presence of intraretinal fluid (*GRADE*: RETFL)
 - Presence of subretinal fluid (*GRADE*: RETFLSF)

- Presence of intraretinal fluid (at least some intraretinal fluid of cystoid origin) (*GRADE*: RETIRC)
- Presence of intraretinal/subretinal fluid within the central subfield (diameter 1000 microns) (*GRADE*: RETSF)
- Presence of PED (*GRADE*: PEDDET)
- Presence of central retinal pigment epithelium (RPE) atrophy (*GRADE*: RPEATRO)
- Presence of macular geographic atrophy (*GRADE*: MACARO)
- Presence of outer retinal tubulations (ORT) (*GRADE*: ORTTUB)
- Presence of vitreomacular traction (*GRADE*: VITTRAC)
- Presence of dry retina. Dry retina is defined as eye without intraretinal fluid (RETFL from derived.grade) AND eye without subretinal fluid (RETFLSF from derived.grade) AND eye without intraretinal cysts (RETIRC from derived.grade)
- Development of RPE rip (*GRADE*: RPETIP)
- Is there atrophy outside the active choroidal neovascularization (CNV) lesion? (*GRADE*: ATROCNV)
- CNV subtype (study eye) (*GRADE*: CNVTYPE)
- Area of macular CNV lesion (standardized) (*GRADE*: AREACNVS)
- Area of leakage (standardized) (*GRADE*: AREALEKS)
- Area of total lesion (including CNV, blood, scar) (*GRADE*: AREATOTS)
- Area size of atrophy (total area) (*GRADE*: AREAATRS)
- From Indocyanine Angiography (ICG):
 - Presence of intraretinal/subretinal or sub-RPE hemorrhage (study eye) (*GRADE*: PRESHEM)
- From General Image Grading:
 - Does the hemorrhage include the fovea (study eye) (*GRADE*: HEMFOV)
 - Presence of active leakage in the sense of a neovascular membrane (study eye) (*GRADE*: LEAKNEO)

Age is calculated in years as (year of drug administration - year of birth)

BMI is calculated as (weight (kg) / [height (cm)/100]²)

All demographic and baseline characteristics details, including derived variables, will be listed.

Age-related macular degeneration diagnosis details, pregnancy test details, historical retinal images details will be listed separately.

2.1.5 Medical history

Relevant medical history (ocular and non-ocular) and current medical conditions will be coded according to the Medical Dictionary for Regulatory Activities (MedDRA) version 18.1 or higher.

Prior to database lock, a complete list of medical history events, as recorded on the eCRF, will be provided by [REDACTED] to Novartis in an Excel spreadsheet. Novartis will review the individual medical history events and classify them as ocular or non-ocular.

The number and percentage of patients with ocular (in study eye and fellow eye) medical histories will be tabulated by system organ class (SOC) and preferred term (PT), by subgroup and overall for the FAS. SOC's will be ordered in decreasing frequency of the total number of patients with ocular medical histories and conditions reported in each SOC and PTs will be ordered within a SOC in decreasing frequency of the total number of patients with ocular medical histories and conditions.

The same table will be provided for ocular current medical conditions, non-ocular medical histories and non-ocular current medical conditions.

All relevant medical history (ocular and non-ocular) and current medical conditions details will be listed.

2.1.6 Prior and concomitant medications

Prior and concomitant medications will be coded according to the World Health Organization Drug dictionary (WHODrug) (Standard) version of September 2015 or higher.

Prior medications are defined as those for which the end date is prior to the date of first dose of study treatment.

Concomitant medications are defined as those which are indicated as 'Ongoing' on the date of first dose of study treatment, or those which start on or after the date of first dose of study treatment, or those which start prior to date of first dose of study treatment and have an end date after the first dose of study treatment.

If medication dates are incomplete and it is not clear whether the medication was concomitant, it will be assumed to be concomitant.

The number and percentage of patients who took any prior medications and the number and percentage of patients who took any concomitant medications will be presented separately by medication class and standardized medication names sorted alphabetically, by subgroup and overall for the SAF.

All prior and concomitant medications will be listed by reported name, medication class, standardized medication name, indication, dose, dose unit, frequency, route of administration, start date and end date or 'ongoing' flag.

2.1.7 Treatment exposure

Treatment exposure to ranibizumab will be summarized by subgroup and overall for the SAF, and will include:

- Duration of exposure to ranibizumab for both study eye and fellow treated eye, as well as total duration of exposure (study eye and fellow eye). Duration of exposure will be calculated as date of last ranibizumab injection – date of first ranibizumab injection + 1, for study eye, fellow treated eye and both eyes together
- Total number of injections overall the study course and number of injections by visit (including unscheduled visits), for both study eye and fellow treated eye
- Number and percentage of patients who received bilateral injections of ranibizumab (both the study eye and fellow eye injected at the same visit) by visit
- Reason for PRN treatment (BCVA decline, or OCT criteria) by visit during the PRN treatment period, for study eye
- Reason for no dosing by visit, for study eye. Prior to database lock, a complete list of reasons for no dosing during the Monthly treatment period, as recorded on the eCRF, will be provided by ██████ to Novartis in an Excel spreadsheet. Novartis will review them and classify them as ocular or non-ocular.
- Compliance to treatment regimen, for study eye

Compliance to treatment regimen will be assessed as follows

- Monthly treatment period, compliance= $100 * (\text{number of injections in study eye} / 3)$
- PRN treatment period, compliance= $100 * (\text{number of injections done in study eye} / \text{number of required injections in study eye based on changes in patient symptoms, BCVA or OCT})$

An injection will be considered as required if:

- in the opinion of the Investigator persistent or worsening visual symptoms are attributed to nAMD and/or
- there is evidence of worsening early treatment diabetic retinopathy study (ETDRS) BCVA (>1 letter decline since last Study Visit) and/or
- the presence of persistent or worsening disease activity on OCT (presence of sub-retinal fluid, persistent or increased number, size or total volume of IRC, or increased central retinal or foveal thickness)

All treatment exposure to ranibizumab details, including derived variables, will be listed.

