## **Compliance to treatment regimen**

The evaluation of compliance will assess whether ranibizumab injections were administered according to the protocol specified regimen during the monthly treatment period and according to the Investigator's assessment of disease activity during the PRN treatment period.

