## **9.3 Treatments**

### **Study treatment**

Descriptive statistics will be provided for exposure to study treatment using the Safety Set, PTF and STR subgroups. The number of ranibizumab injections will be presented by visit and cumulatively. Summaries will be presented for the injections in the study eye and the fellow treated eye as appropriate. Other data related to the application procedure will be summarized as appropriate.

The proportion of patients who received bilateral injections of ranibizumab (both the study eye and fellow eye injected at the same visit) will be summarized by visit.

Analyses of the treatment exposure will include:

- Treatment frequency (total number of injections and number of injections by visit)
- Reason for PRN treatment (patient symptoms, BCVA decline, or OCT criteria)
- Compliance to treatment regimen (if treatment given monthly per protocol or as a response to changes in patient symptoms, BCVA or OCT)

Reasons for discontinuation from the study will be summarized.

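### SAP 2.1.7 gives symptom-driven PRN injections no reason category and computes PRN compliance from period totals that are not matched by visit (minor)

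*SAP*

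**What the plan says.** **Protocol.** Section 6.3 says PRN compliance will assess whether injections were given "according to the Investigator's assessment of disease activity during the PRN treatment period". Section 9.3 lists among the exposure analyses "Compliance to treatment regimen (if treatment given monthly per protocol or as a response to changes in patient symptoms, BCVA or OCT", and also "Reason for PRN treatment (patient symptoms, BCVA decline, or OCT criteria". Sections 3.1 and 5.5.4.2 give three alternative grounds for re-treatment: visual symptoms attributed to nAMD, a BCVA decline of more than 1 letter since the last visit, and OCT activity. The footnote defining OCT activity names several findings and ends with an open limb that admits comparable quantitative imaging data in the patient's record.

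**SAP 2.1.7.** PRN compliance is 100 times the injections done in the study eye divided by the "number of required injections in study eye based on changes in patient symptoms, BCVA or OCT". An injection counts as required if any of three criteria is met. The first is "in the opinion of the Investigator persistent or worsening visual symptoms are attributed to nAMD and/or"; the others are BCVA decline and OCT activity. The OCT criterion carries a list of findings in parentheses without the protocol's open limb. The reason summary, however, is "Reason for PRN treatment (BCVA decline, or OCT criteria) by visit during the PRN treatment period, for study eye". The section also plans "Reason for no dosing by visit, for study eye", and says "All treatment exposure to ranibizumab details, including derived variables, will be listed".

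**The concern.** There are two faults in one section of the SAP.

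First, the reason table offers two categories where Protocol 9.3 has three. An injection given for symptoms alone has nowhere to go, although the same SAP section treats symptoms as enough to make an injection required. Such injections would be left out or placed under a heading that does not describe them.

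Second, the protocol describes whether treatment followed the assessment, which is a question about each visit. The SAP answers with two totals over the period. Totals can agree when the visits do not, can exceed 100%, and give no value for a patient who never needed an injection and correctly received none. A reader of the study report would take 100% to mean that injections were given when indicated, and the formula does not guarantee that.

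**Working it through.** The documents state no compliance figure, so there is none to reproduce. The check compares the texts and then applies the SAP formula to every possible pattern.

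**1. Reasons for PRN treatment.**
- Protocol 9.3: symptoms, BCVA decline, OCT.
- SAP 2.1.7, required-injection list: symptoms, BCVA decline, OCT.
- SAP 2.1.7, reason table: BCVA decline, OCT.

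The reason table disagrees with the protocol and with its own section.

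**2. The ratio.** Inputs: three PRN decision visits, Days 90, 120 and 150 (Protocol 3.1, 5.5.4.2 and Table 6-2). At each visit, r = 1 if an SAP criterion is met and g = 1 if an injection is given. R is the sum of r and G the sum of g. Per patient, compliance = 100 × G/R.

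Examples:
- No criterion met, no injection: 0/0, no value.
- Required only at Day 90, injected only at Day 120: 100 × 1/1 = 100%, with 2 of 3 visits discordant.
- Required only at Day 90, injected at Days 90 and 120: 100 × 2/1 = 200%.

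All patterns, 8 × 8 = 64:

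| Result | Patterns |
|---|---|
| 100%, every visit matches (r = g) | 7 |
| 100%, visits do not match | 12 |
| Above 100% (G > R > 0) | 15 |
| Below 100% (G < R) | 22 |
| Injected, none required (k/0) | 7 |
| Neither required nor injected (0/0) | 1 |
| Total | 64 |

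Thus 12 of the 7 + 12 = 19 patterns scoring exactly 100% do so with injections at visits other than those required. These are counts of possible patterns, not expected frequencies.

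**3. What drives the errors.** Keep only the patterns in which every injection had an SAP criterion at that visit (g ≤ r throughout): 3 × 3 × 3 = 27. Of these, 7 are a true 100%, 19 are below 100% and one is 0/0. None is a false 100% and none exceeds 100%. So 0/0 arises in any case, while offsetting, values above 100% and k/0 all need an injection at a visit with no SAP-listed criterion.

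**4. Whether that needs a deviation.** Protocol 5.5.4.2 requires source evidence of at least one re-treatment criterion, which at first seems to rule such injections out. But an injection supported only by the protocol's open OCT limb satisfies the protocol and, if the SAP's list is read as complete, is not required under the SAP. In the 200% example, a Day 120 injection on that ground is enough. If the Day 90 injection in the 100% example was not given, through Investigator discretion or withholding under Protocol 5.5.5, that false 100% also arises without a deviation.

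**5. Restricting the numerator to required visits.** Of the 64 patterns, 8 have no value (R = 0), 19 give 100% and 37 fall below. Offsetting and values above 100% disappear. The 0/0 case remains, and 19 − 7 = 12 of the 100% patterns contain an extra injection that the ratio no longer shows.

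**The case against.** The best defence is that neither Protocol 6.3 nor 9.3 prescribes a visit-level metric, and that the SAP uses the same three criteria. The numerator may have been meant to count only injections given when required, and then offsetting goes. A 0/0 patient would probably just drop out of n, which SAP section 2 defines as the number of non-missing observations. Injections, reasons and non-dosing are already tabulated by visit and listed, all deviations are listed, and the deviation appendix, which is not shown, may cover PRN departures by visit. The parenthesis after the OCT criterion could be illustrative. Two entries in the SAP's list of changes from the protocol are redacted, so removal of the symptom category may have been declared.

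Much of this stands, and it limits the size of the point. It does not remove it. The SAP does not state the restricted numerator or any rule for a zero denominator, and a declared change would still leave the reason table at odds with the required-injection list beside it.

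A reader might also infer more than the documents support:
- **That the ratio may be pooled over patients, so errors cancel between them.** The monthly formula alongside divides by 3, which only makes sense per patient.
- **That Day 180 counts as a decision visit and lowers the score of fully treated patients.** Protocol 3.1 and 5.5.4.2 end PRN decisions at Day 150, and Table 6-2 marks no injection at Day 180.
- **That the status of withheld injections is undefined.** Under the SAP rule they are required and not done, and the planned reasons for no dosing explain them.
- **That a met criterion with no injection is non-compliance.** Protocol 3.1 leaves the decision to the Investigator, and 5.5.4.2 says the regimen permits re-treatment.

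**Conclusion.** The concern holds as a minor point about descriptive exposure outputs. The reason table is incomplete against Protocol 9.3 and inconsistent within SAP 2.1.7. The compliance ratio does not show whether injections followed the assessments, and it has no value for a patient who correctly received none.

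The primary Day 90 CSRT result is unaffected: Protocol 6.4 places efficacy assessments before the injection at each visit, so PRN treatment begins after the primary measurement.

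How often the ratio would mislead cannot be said, because the documents give no rates for criteria met, injections missed or injections given outside the SAP list. The conclusion assumes a per-patient ratio, a literal reading of the formula and three decision visits. The claim that values above 100% or a false 100% can occur without a deviation also assumes that the SAP's OCT list is exhaustive.

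**What to change.** 1. Restore patient symptoms as a PRN-reason category, or state why it was removed. First check how symptoms are captured: Protocol 6.3 puts the reason for dosing and the BCVA and OCT disease activity on the eCRF but does not name symptoms.
2. Align the OCT criterion in the SAP's required-injection list with the protocol's definition, so that the analysis applies the rule given to sites.
3. Replace or supplement the ratio with a table of criterion met or not met by injected or not injected at each scheduled PRN decision visit. Split the cell for met but not injected by the recorded reason for no dosing, and do not label it non-compliance by default.
4. Reconcile the decision visits before programming: Protocol 3.1, 5.5.4.2 and Table 6-2 run through Day 150, while Protocol 5.3 names only Days 90 and 120.
5. If the ratio is kept, count only injections at visits where one was required, and show patients with no required injection as not applicable, with their number. Keep the table beside it, since this ratio hides injections given with no listed criterion.

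The cost is SAP wording and one extra table, plus the editorial reconciliation in the protocol. No new data collection is needed unless the eCRF check shows that symptom status was not recorded by visit; it would then have to come from the recorded reason for dosing or from source documents.
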